#### *Glycemic control*

HbA1c was collected from blood samples at baseline, 12 and 24 weeks. Time spent in range (TIR) 70-180 mg/dl assessed by CGM was downloaded at each visit with the dietician. Severe hypoglycemia was defined as an episode requiring assistance and was confirmed by documentation of a blood glucose value less than 54 mg per deciliter.

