and qualitatively for physical activity and pre-meal blood glucose levels. Overall, it was found that conventional therapy resulted in suboptimal insulin counteraction of postprandial glycemic responses. More sophisticated models exist, such as those that also adjust to the fat content of the meal, but so far, they have failed to provide a significant improvement in glycemic control, and are recommended by the ADA only for advanced patients.

Carbohydrates are the primary macronutrients that affect the postprandial glycemic response. Given the difficulty of matching carbohydrate intake with insulin dose, reducing dietary carbohydrate consumption among people with diabetes is becoming a common diet pattern. Essentially, the lower the glycemic response, the less insulin is administered, and the lower the fluctuations of blood glucose levels in absolute terms. Although low carbohydrate diet (LCD) has a promising effect on glycemic control and is popularized both by social media and the patients, it is poorly studied and may lead to harmful dietary consequences. Carbohydrate-containing foods including grains, fruit and milk, are important sources of nutrients. Hence, low-carbohydrate diet requires attention to vitamin and energy intake to avoid micronutrient deficiencies and growth issues. Adherence to restricted diets is challenging and can have an impact on social normality. In individuals with T1DM, adverse health risks such as diabetic ketoacidosis, hypoglycemia, dyslipidemia and glycogen depletion remain clinical concerns. Parents who decide to put their child on such a regime, usually do it without proper medical guidance and may put their child at risk of nutritional depletion of essential nutrients and minerals. Studies looking at glycemic outcomes from low-carbohydrate diets have largely been cross-sectional, without validated dietary data and with a lack of a control group.

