Composition, alteration, and diversity of the gut microbiota might affect the glycemic control. Dysbiosis and changes in the properties of the gut barrier have been documented in T1DM subjects. The common finding in all of these studies is the increased proportion of Bacteroides bacteria which appear at the time of the initial diagnosis and tend to decrease over time, but without reaching the levels of healthy children. According to a recent study in T1DM children, changes in diet directly influenced the intestinal microbiota composition, and therefore might correct the gut dysbiosis in patients with T1D. These results show the merit of studying the microbiome of already diagnosed T1D patients, with the prospect of performing microbiome interventions aimed at improving glycemic control.

We propose an integrated study examining the effect of the LCD versus the Mediterranean diet (MD) upon both the glycemic control and on the gut microbiome. In order to isolate the effect of intensive dietary intervention, we will compare LCD to MD. The MD has been widely reported as one of the healthiest models for preventing cardiovascular disease and beneficial

for HbA1c. The SEARCH Nutrition Ancillary Study concluded that a higher MD score was associated with better glycemic control and lipid profile in youth with T1D. To the best of our knowledge, this will be the first controlled study upon adolescents with T1D on a low carbohydrate diet.

According to most recent data reported, only a minority of individuals meet ADA ( American Diabetic Association) HbA1c goals and HbA1c levels remain particularly high in adolescents and young adults. Parents and patients who may consider LCD as an option to optimize glycemic control face many concerns including hypoglycemia, ketoacidosis, nutritional insufficiency, poor growth, inadequate bone mineralization, poor metabolic profile, and psychological consideration due to the lack of data. Because more patients are choosing to follow a carbohydrate-restricted diet, there is a need to evaluate benefits and risks of LCD vs. MD among youth with T1DM after consuming LCD.

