### Secondary end points

1. Evaluation of the influence of LCD vs. MD on HbA1c, insulin dose (average total daily dose/ kg), glycemic variability (TIR, Time below 54 mg/dl, CV- Coefficient Variant) and average blood glucose.
2. Assessment of the impact of dietary changes after an LCD vs. MD on gut dysbiosis.
3. Assessment of the impact of both diets on bone turnover measures, lipid profile, vitamin levels, weight and height.
4. Assessment of the impact of dietary changes after an LCD vs. MD on quality of life.

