### **Methods:**

#### **Participants and study design**

Adolescents with T1DM will be enrolled at the Pediatric Endocrinology and Diabetes unit of the Edmond and Lily Safra Children's Hospital, Sheba Medical Center (Ramat Gan, Israel). Written informed consent was obtained from participants age  $\geq 18$  years or their parents or legal guardians if  $< 18$  years. Ethic approval and monitoring is obtained from the Helsinki Committee in Sheba Hospital.

The study design is a randomized, parallel assignment clinical trial without blinding (open label) due to the impracticality of blinding diets. The criteria for eligibility are: age between 12 to 22 years, presence of T1DM (according to the American Diabetes Association criteria) for at least one year, and usage of a CGMS (Dexcom, Medtronic, Libre) device. Exclusion criteria included medical history of eating disorders or any other mental illness.

Participants who will meet all inclusion criteria will be randomly assigned to either the intervention (LCD) diet group or to the MD group in a 1:1. Randomization assignments were computer generated by the study statistician prior to the start of the study using random permuted block sizes of 2 or 4.

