#### *Glycemic variability*

Glycemic variability from continuous blood glucose monitoring (Libre, Medtronic, Dexcom) and included SD Time spent in range 70-180 mg/dl, Time between 70-54mg/dl, time under 54 mg/dl and CV (coefficient variant) assessed by CGM was downloaded at each visit (baseline, and weeks 1,2,4,7,10 and 12) with the dietician.

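### The severe-hypoglycemia definition requires a documented glucose below 54 mg/dl, so assisted episodes without such a value may go uncounted and the absolute count can be biased low

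*Protocol*

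**What the plan says.** The protocol defines severe hypoglycemia once, under Glycemic control: "Severe hypoglycemia was defined as an episode requiring assistance and was confirmed by documentation of a blood glucose value less than 54 mg per deciliter". It gives no second route for an assisted episode that lacks such a value.

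Hypoglycemia is among the risks that motivate the trial. The Introduction says that "adverse health risks such as diabetic ketoacidosis, hypoglycemia, dyslipidemia and glycogen depletion remain clinical concerns" and concludes that "there is a need to evaluate benefits and risks of LCD vs. MD among youth with T1DM after consuming LCD".

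Severe hypoglycemia is not a listed endpoint, and the Statistical Analysis section does not mention it. The hypoglycemia measure under Secondary end points is a sensor measure, within "glycemic variability (TIR, Time below 54 mg/dl, CV- Coefficient Variant) and average blood glucose". The Glycemic variability section collects "Time between 70-54mg/dl, time under 54 mg/dl and CV (coefficient variant) assessed by CGM". Eligibility requires "usage of a CGMS (Dexcom, Medtronic, Libre) device", so every participant wears a sensor.

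**The concern.** The definition joins need for assistance and a documented low value with *and*. Three kinds of assisted episode then fall outside it:

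- the participant is treated before anyone measures;
- the first value is taken after treatment and is no longer below 54 mg/dl;
- help was needed at a value of 54 mg/dl or above.

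The first two can arise in an emergency, when treatment comes before measurement. Some of the more serious episodes may therefore be the ones left out.

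What is at stake is the absolute number of severe episodes reported for each diet. This is the protocol's only event-based definition of hypoglycemia. In a trial of 40 participants the count is likely to be small, so one or two missing events would change what a reader learns about a risk that the protocol itself names.

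**Working it through.** **No figure to reproduce.** The protocol gives neither an expected rate of severe hypoglycemia nor a rate at which assisted episodes have a documented value. The check is a logical one, followed by a range under stated assumptions.

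**Step 1: what is counted.** Counted events are assisted episodes that also have a documented glucose below 54 mg/dl. This is a subset of all assisted episodes, so the count cannot exceed the number of assisted episodes and falls short whenever one lacks a qualifying value. The direction follows from the wording alone.

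**Step 2: size under an assumed share.** Let T be the number of true assisted hypoglycemic episodes and d the share with a qualifying value. Then:

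- expected count = d × T, a relative change of (d − 1) × 100%;
- chance that at least one of k episodes is lost = 1 − d^k, taking episodes as independent.

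The values of d and k are assumptions.

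| d | Change in expected count | At least one lost, k = 2 | At least one lost, k = 4 |
|---|---|---|---|
| 1.00 | 0% | 0% | 0% |
| 0.95 | −5% | 9.8% | 18.5% |
| 0.90 | −10% | 19% | 34.4% |
| 0.80 | −20% | 36% | 59% |
| 0.70 | −30% | 51% | 76% |

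As an extreme case, d = 0.50 gives 4 × 0.5 = 2 expected counted episodes out of 4. Two true episodes in one arm would then be reported as none with probability 0.5 × 0.5 = 25%.

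**Step 3: the comparison between diets.** The observed rate ratio is the true ratio multiplied by d(LCD) / d(MD).

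- Equal shares, such as 0.9 and 0.9: multiplier 1.0, no bias.
- 0.9 against 0.8: 0.9 / 0.8 = 1.125.
- 0.8 against 0.9: 0.8 / 0.9 = 0.889.

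The ratio moves only if documentation differs by arm, and then in either direction.

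**Step 4: does the sensor endpoint fill the gap?** Time below 54 mg/dl is obtained whether or not anyone helped, so it captures low glucose that the event definition misses. It does not record whether help was needed, so it cannot recover an uncounted assisted episode. A full trace also does not bring in an assisted episode at 54 mg/dl or above. Coverage is not clear for the whole trial either: Glycemic variability lists downloads at baseline and up to week 12, whereas Glycemic control says each dietitian visit, and Diet intervention places one of those at week 24.

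**The case against.** The strongest case against the point has five parts.

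1. **Universal CGM.** A trace will often exist even when helpers treat first. Glycemic variability describes these devices as monitoring blood glucose, so in the protocol's own usage a sensor value may well qualify. This stands in part. It reduces the likely loss and weakens any claim that only meter values count. But the definition does not say that sensor values are accepted, and it still excludes assisted episodes at 54 mg/dl or above.
2. **Confirmation buys specificity.** Requiring a value also screens out assisted episodes of another cause. This is true, and it is why the confirmed episodes should remain visible as a subset.
3. **The wording may describe verification, not exclusion.** On that reading unconfirmed episodes might still be recorded, and the event form or an analysis plan that is not at hand might say how. This is possible. But the definition itself is fixed in the protocol, its natural reading is conjunctive, and two staff members could classify the same episode differently.
4. **Bias between diets.** A reader might infer from the open-label design that one arm's episodes would be better documented. The documents do not support that: Diet intervention gives all participants the same meetings and telephone calls, with equal intensity as the stated aim.
5. **Few events decide little.** With an assumed 20 per arm, 2 events against 0 gives a two-sided Fisher p of 2 × (20 × 19) / (40 × 39) = 0.49. Losing them would not overturn a statistical conclusion. This stands. The harm is to the descriptive safety record, not to a test.

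**Conclusion.** The point holds as a weakness of the outcome definition. As worded, an assisted episode counts only with a documented glucose below 54 mg/dl, so the absolute count of severe hypoglycemia can be biased low and cannot be biased high relative to all assisted episodes.

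The size is unknown. A loss of 0% to 30% corresponds to assumed documented shares of 1.0 to 0.7, and nothing in the protocol narrows that range.

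Two further stronger readings should be avoided. A reader might infer that severe hypoglycemia is the trial's main safety outcome; the protocol neither lists it as an endpoint nor ranks its safety measures. A reader might also infer that real episodes are certain to be lost; that depends on how often a qualifying value is missing, which the documents do not say.

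The primary time-in-range analysis and the sample size are not affected. The change is still worth making, because the protocol sets out to weigh risks as well as benefits and the correction is cheap.

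**What to change.** Change the outcome definition and its reporting only; no treatment rule is involved.

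- Count, and report by arm, every episode of hypoglycemia in which the participant needed another person's assistance, whether or not a glucose value was documented.
- For each episode record the glucose value and its source (meter or CGM), classified as below 54 mg/dl, 54 mg/dl or above, or not available.
- State that CGM values count as documentation.
- Report the episodes confirmed below 54 mg/dl as a subset, so that the count under the present definition is kept.

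The cost is a short change of protocol wording and a glucose value-and-source entry on the event form. The downside is that a few unconfirmed episodes of other cause may be counted; showing the confirmed subset beside the total makes these visible.

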#### *Glycemic variability*

Glycemic variability from continuous blood glucose monitoring (Libre, Medtronic, Dexcom) and included SD Time spent in range 70-180 mg/dl, Time between 70-54mg/dl, time under 54 mg/dl and CV (coefficient variant) assessed by CGM was downloaded at each visit (baseline, and weeks 1,2,4,7,10 and 12) with the dietician.

#### *Anthropometric Measurement*

At the beginning of each meeting with the dietician the following data were collected: height, weight, waist circumference, blood pressure and pulse rate. All were measured according to

standardized protocol by trained and certified staff. Body mass index (BMI), is calculated as weight (kg)/height squared (m^2).

### *Biochemical Parameters*

Fingertip blood samples will be collected and processed for measurements of ketones (Beta-hydroxybutyrate) with Abbott Freestyle Optium Neo- Blood Glucose & Ketone test meter at each visit held with the dietician.

Blood samples including; HbA1c, zinc (Atomic absorption with flame technique) , vitamin C, lipid profile, creatinine, folic acid, thiamin, magnesium, vitamin C, transferrin, ferritin, zinc, carnitine, copper, CRP, TSH, FT4, were collected under metabolic stability conditions, defined as no episode of diabetic ketoacidosis within 1 month before the visit, and after  $\geq 12$  hours of fasting. All fasting blood samples will be taken at baseline, 12- and 24-weeks from a forearm vein and processed at the Sheba Medical Center laboratories.

### *Assessment of bone turnover markers*

Blood samples were obtained from the participants after a 12-hr fast at baseline, 12 and 24 weeks. Bone markers: procollagen type 1 amino-terminal propeptide (P1NP) and bone resorption C-terminal telopeptide of type 1 collagen (CTX1) were measured using ELISA method.

### *DNA extraction, PCR amplification, and sequencing*

Fresh fecal samples were collected during weeks 1,4 and the last week of the experiment for the gut microbial 78 characterization. Bacterial genomic DNA was extracted from frozen fecal samples stored at  $-80^{\circ}\text{C}$ . 79 DNA extraction and PCR amplification of the variable region 4 (V4) of the 16S rRNA gene using 80 Illumina adapted universal primers 515F/806R was conducted using the direct PCR protocol 81 [Extract-N-Amp Plant PCR kit (Sigma-Aldrich, Inc.)] as previously described . Briefly, PCRs were 82 conducted in triplicate in a 96 well plate [denaturation for 3 min at  $94^{\circ}\text{C}$ ; 35 cycles ( $98^{\circ}\text{C}$ , 60 s;  $55^{\circ}\text{C}$ , 83 60 s;  $72^{\circ}\text{C}$ , 60 s) followed by elongation for 10 min at  $72^{\circ}\text{C}$ ]. Positive amplicons were pooled in 84 equimolar concentrations into a composite sample that was size selected (300–500 bp) using agarose 85 gel to reduce non-specific products from host DNA. Sequencing was performed on the Illumina 86 MiSeq platform with addition of 20% PhiX, and generating paired-end reads of 175b in length in 87 each direction.

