### **Diet intervention**

In order to maintain equal intensity of treatment, each patient will take a cooking workshop and receive a personalized diet regime at baseline, based on the randomly assigned diet. Format and quality of the materials were similar. (Appendix 1)

All diet plans will be individualized and matched for energy intake personally.

*Low carbohydrate diet*- The low carbohydrate diet aims to provide 50-80g of carbohydrate per a day. Planned macronutrient compositions (percentage from total calories) of the diet: 15% carbohydrate (<80 g/day), 33% protein and 58% total fat.

*Mediterranean diet*-The moderate-fat Mediterranean diet is rich in vegetables and low in red meat, with poultry and fish replacing beef and lamb. The main sources of added fat were 30 to 45 g of olive oil and a handful of nuts (five to seven nuts <20g) per day. The planned macronutrient compositions of the diet were 50% carbohydrate, 25% protein and 35% total fat. The diet is based on the recommendations of Willett and Skerrett.

Participants will meet individually with the dietitian for diet instruction and support at week 1,2,4,7,10,12 and thereafter at 24 weeks for a total of seven frontal meetings. Twice during the first 12 weeks the dietitian will conduct 10-15-minute motivational telephone calls with all the participants.

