## **Statistical Analysis**

The sample size was based on the primary endpoint, ie delta in the time spent in range (TIR 70-180 mg/dl). To be able to detect a difference of 20% with 80% power at a 5% significance level with a two-sided paired t-test. Thirty-four participants should complete the study. To account a 40% attrition rate, we included a total of 40 participants in the study. The sample size was calculated using PASS 2020 software.

Data will be analyzed with the IBM SPSS software (IBM SPSS Statistics for Windows, Version 24;IBM Crop., Armonk, NY, USA, 2016). Categorical variables were assessed for frequency and percent. Continuous variables described as frequency and percent. Continuous variables were assessed for normal distribution using histogram and Q-Q plots. Normally distributed continuous variables were described as means and standard deviations (SD), and non-normally distributed parameters were described as median and interquartile rang (IQR). Categorical variables in the same group were compared using a dependent sample t test. Differences between groups in continuous data were compared using independent-sample t tests (normally distributed data) or Mann-Whitney test (skewed data). For variables that were non-normally distributed, the median interquartile range (IQR) were presented and Kruskal-Wallis test was applied to evaluate he differences.

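### No stool sample is scheduled before the assigned diet is handed out, so the gut-dysbiosis endpoint has no pre-diet reference

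*Protocol*

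**What the plan says.** Secondary end point 2 in the Protocol reads "Assessment of the impact of dietary changes after an LCD vs. MD on gut dysbiosis". The section on DNA extraction, PCR amplification and sequencing sets the collection times: "Fresh fecal samples were collected during weeks 1,4 and the last week of the experiment". It names no baseline collection, and no other section does.

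Under Diet intervention, "each patient will take a cooking workshop and receive a personalized diet regime at baseline". The same section puts the dietitian meetings "at week 1,2,4,7,10,12 and thereafter at 24 weeks for a total of seven frontal meetings". The Glycemic variability section says that CGM data "was downloaded at each visit (baseline, and weeks 1,2,4,7,10 and 12) with the dietician", which treats baseline and week 1 as two time points.

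Other outcomes have an explicit baseline. For bone markers, "Blood samples were obtained from the participants after a 12-hr fast at baseline, 12 and 24 weeks". HbA1c, the fasting biochemistry, the food-frequency questionnaire, the self-efficacy scales and the DQOL are likewise scheduled at baseline, 12 and 24 weeks.

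**The concern.** As written, the diet is handed out at baseline and the first stool sample comes during week 1. That sample may already carry part of the diet's effect. The Introduction argues that diet acts directly on gut bacteria and might correct an existing dysbiosis. Whether a dysbiosis was corrected is a question about change from the pre-diet state, and no scheduled sample is stated to measure that state.

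Three things are at stake:

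- a description of the participants' microbiome before the diet, including any chance imbalance between two small arms;
- change from that state within each arm;
- adjustment of the between-arm comparison for a true baseline value.

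Week 1 is not a safe substitute. An analysis that took it as the reference would subtract whatever part of the effect was already present, and so would understate a lasting early effect. The protocol states no such analysis and gives no time course, so the size of that loss is unknown.

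This is a matter of when specimens are collected, which the protocol fixes. No SAP can restore a sample that was not taken.

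**Working it through.** **Timing.** The relevant sections, side by side:

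| Item | Time points | Protocol section |
|---|---|---|
| Assigned diet plan and workshop | Baseline | Diet intervention |
| Dietitian meetings | Weeks 1, 2, 4, 7, 10, 12, 24 (7 meetings) | Diet intervention |
| CGM downloads at visits | Baseline and weeks 1, 2, 4, 7, 10, 12 (7 visits) | Glycemic variability |
| Fasting blood | Baseline, weeks 12 and 24 | Biochemical Parameters |
| Bone markers | Baseline, weeks 12 and 24 | Assessment of bone turnover markers |
| FFQ, self-efficacy, DQOL | Baseline, weeks 12 and 24 | Questionnaires |
| Stool | Weeks 1, 4 and the last week | DNA extraction, PCR amplification, and sequencing |

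Of the three scheduled stool samples, none is stated to precede the diet. The two visit lists disagree. Adding week 24 to the CGM list gives 7 + 1 = 8 visits, against seven meetings under Diet intervention. The protocol is therefore not consistent on whether baseline and week 1 coincide. Under either reading, nothing places the week-1 stool before the diet is given.

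**Precision.** The protocol gives no figure for this endpoint, so there is nothing to reproduce. The inputs are:

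- Completers: "Thirty-four participants should complete the study" (Statistical Analysis).
- Allocation: "randomly assigned to either the intervention (LCD) diet group or to the MD group in a 1:1" (Participants and study design), hence 34 / 2 = 17 per arm.
- Two-sided 5% level and 80% power, borrowed from the protocol's sample-size statement for the primary endpoint.
- Correlation ρ between the pre-diet and follow-up values: not given. Assumed 0.3, 0.5 and 0.7.

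For a two-sample t test, the detectable standardised difference d solves

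P(|T| > t₀.₉₇₅,df) = 0.80, where T is noncentral t with noncentrality d·√(n/2).

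Unadjusted, with n = 17 and df = 32: d = 0.991.

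With the pre-diet value as a covariate, df = 31 and the residual SD is √(1 − ρ²) times the raw SD. Solving at df = 31 gives 0.992, which is then multiplied by √(1 − ρ²). The last column is the unadjusted n per arm that would detect the same difference.

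| ρ | √(1 − ρ²) | Detectable difference (raw SD) | Unadjusted n per arm for the same difference |
|---|---|---|---|
| 0 | 1.000 | 0.992 | 17 (no gain) |
| 0.3 | 0.954 | 0.946 | 18.5, so 19 |
| 0.5 | 0.866 | 0.859 | 22.3, so 23 |
| 0.7 | 0.714 | 0.708 | 32.3, so 33 |

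**Fewer completers.** The protocol enrols 40 and cites 40% attrition. Taken literally, that leaves 40 × 0.60 = 24 completers, or 12 per arm. The unadjusted detectable difference is then 1.20 SD. Adjusted, with df = 21, it is 1.14, 1.04 or 0.86 SD at the same three correlations.

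**The case against.** The strongest reply is that week 1 may simply be the start-of-study visit. Stool is taken during week 1, which could include the day the diet is handed out. The count of seven dietitian meetings starts at week 1 and leaves no separate baseline meeting. This reading is possible and limits how firmly one can say that the first sample comes after the diet. It does not close the gap: the CGM visit list separates the two time points, and even if they coincide, nothing says stool is taken before the workshop and diet plan.

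Second, the endpoint compares two randomised arms, and a follow-up comparison needs no baseline. That stands. The protocol does not define a change-from-baseline microbiome measure either. The endpoint is weakened, not invalid.

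Third, the precision figures are hypothetical. No correlation or microbiome metric is given, the gain is small at ρ = 0.3, and the Statistical Analysis section mentions no covariate adjustment. This also stands. The figures show what a pre-diet sample could buy, not what it will buy. They also rest on 34 completers, which is optimistic if attrition reaches the stated 40%.

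Fourth, a week-1 reference understates the effect only if the early response lasts. If the response is transient or overshoots, the distortion could go either way. That is fair, and it is a further reason not to use week 1 as the reference.

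**Conclusion.** The concern holds. The protocol schedules no stool sample that it places before the diet, although it names a baseline for its other laboratory and questionnaire outcomes. The between-arm comparison at week 4 and the last week survives, and change between the scheduled samples can be observed. The pre-diet state, change from it, and adjustment for it are lost for good.

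For one continuous measure and 17 per arm, the possible precision loss runs from nil at a correlation near 0 to the difference between 0.99 and 0.71 SD at 0.7. That range rests on the assumed correlations and on 34 completers split evenly. The remaining uncertainty is whether week 1 was meant as baseline, which the protocol leaves unresolved. This should be changed because it is cheap and cannot be repaired later, but it does not threaten the validity of the trial.

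**What to change.** Move the week-1 stool collection to the baseline visit and state that it is taken before the workshop and diet plan are given. Keep the week-4 and last-week collections. Compare the arms on follow-up microbiome measures adjusted for the pre-diet sample.

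If baseline and week 1 are meant to be one visit, no move is needed. Say so in the stool-sampling section, state that stool is taken before the diet is handed out, and bring the visit lists under Diet intervention and Glycemic variability into line.

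The cost is schedule wording, with the same three samples per participant. The downside of moving the sample is that the week-1 response is no longer observed. Keeping it as well would mean four samples per participant instead of three.
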